4.5.16 Optional CSF Collection

Patients for whom screening CSF was collected will have the option to participate in a collection of CSF at Week 48 of the double-blind treatment phase; this sample will be used for exploratory biomarker determination that may include, but may not be limited to, NfL (see Section 3.4.5). The CSF sample should be collected prior to the ocrelizumab (or placebo) infusion at Week 48 (within a window of 14 days prior to the actual scheduled visit Week 48; see [Appendix 1](#)).

4.6 OVERVIEW OF CLINICAL VISITS

After the screening, patients who fulfill the entry criteria will be scheduled for baseline assessments. Visits will take place as described in [Appendix 1](#), [Appendix 2](#), [Appendix 3](#), and [Appendix 4](#).

Visits should be scheduled with reference to the date of the baseline visit (Day 1). A minimum interval of 20 or 22 weeks, depending if the previous dose was administered in one or two infusions as per Section 3.1.1.2, Section 3.1.1.3, and Section 3.1.1.5, respectively, should be maintained between each infusion.

At infusion visits, it is anticipated that the patients will have to stay at the hospital or clinic for a full day. Patients treated with ocrelizumab should remain in observation for at least 1 hour after the completion of the infusion. If for logistical reasons the infusion cannot be administered on the same study visit day, the infusion should be given within the next 24 hours provided that the patient still meets re-treatment criteria.

Patients who cannot receive their infusion at the scheduled visit or within 24 hours of the visit should be rescheduled for a delayed dosing visit (see Section 4.6.1). Additional unscheduled visits for the assessment of disease worsening, new neurological symptoms, or safety events may occur at any time.

Patients who are pregnant and breastfeeding should continue to follow the schedule of activities; however, no infusions will occur. If there is a concern with the ability of a pregnant or breastfeeding patient to complete all scheduled assessments, or if assessments are contraindicated with pregnancy, the investigator must contact the Medical Monitor for further discussion.

4.6.1 Delayed Dosing Visit

Delayed dosing visits may be scheduled only if the infusion cannot be administered at the timepoints defined in the schedules of activities (see [Appendix 1](#), [Appendix 2](#),

Appendix 3, and Appendix 4). Thus, a patient who had all assessments of a dosing visit performed, but could not receive the infusion, should be rescheduled for the infusion on another day. At the delayed dosing visit, additional tests or assessments, such as routine safety laboratory tests, may be performed as clinically indicated.

4.6.2 Unscheduled Visits

Patients who develop new or worsening neurological symptoms should be seen at the investigational site as soon as possible, regardless of the dates of their pre-planned, scheduled study visits and regardless of the study period. The EDSS assessment should be performed for any suspected neurological worsening. If an MS relapse is diagnosed or suspected, EDSS assessment should be performed within 7 days, in addition to completing the appropriate eCRF.

Other assessments performed at unscheduled (non-dosing) visits will depend on the clinical needs of the patient. The primary reason for performing an unscheduled visit will be reported in the eCRF.

4.7 TREATMENT, PATIENT, STUDY, AND SITE DISCONTINUATION

4.7.1 Study Treatment Discontinuation

Patients must permanently discontinue study treatment if they experience any of the following:

- Any medical condition that the investigator determines may jeopardize the patient's safety if he or she continues to receive study treatment
- Investigator determines it is in the best interest of the patient

Additionally, patients must be withdrawn from treatment under the following circumstances:

- Life-threatening (National Cancer Institute Common Terminology Criteria for Adverse Events [NCI CTCAE] Grade 4) infusion-related event that occurred during a previous ocrelizumab infusion
- Demonstrate active hepatitis B infection, either new onset or reactivation
- PML
- Patients who decide to discontinue the treatment

The primary reason for study treatment discontinuation should be documented on the appropriate eCRF. Patients who discontinue study treatment prematurely will not be replaced.

An excessive rate of treatment withdrawals can render the study non-interpretable; therefore, unnecessary treatment withdrawal of patients should be avoided.

If a patient meets any of the treatment withdrawal criteria (see above), the patient must be withdrawn from treatment. Patients who prematurely withdraw from study drug treatment will need to return to the clinic for a treatment discontinuation visit (see [Appendix 1](#), [Appendix 2](#), and [Appendix 3](#) for additional details). After treatment discontinuation, every effort should be made to have the patient enter the follow-up phase of the study (FU1 or FU2).

For patients who have withdrawn from study drug treatment, the investigator should decide as to further treatment of the underlying disease (see Section [4.4.3](#) for recommendations on alternative treatments for MS post-ocrelizumab).

4.7.2 Patient Discontinuation from Study

Patients will return to the clinic for an end of observation or withdrawal from follow-up visit.

Patients have the right to voluntarily withdraw from the study at any time for any reason. In addition, the investigator has the right to withdraw a patient from the study at any time. Reasons for withdrawal from the study may include, but are not limited to, the following:

- Patient withdrawal of consent
- Study termination or site closure

Every effort should be made to obtain information on patients who withdraw from the study. The primary reason for withdrawal from the study should be documented on the appropriate eCRF. If a patient requests to be withdrawn from the study, this request must be documented in the source documents and signed by the investigator. Patients who withdraw from the study will not be replaced.

Patients who withdraw from study drug treatment during any study period, for any reason, are encouraged to enter and complete the applicable follow-up phase (see Section [4.7.1](#)). Patients who withdraw from FU1 or FU2 will return to the clinic for a withdrawal from follow-up visit (see [Appendix 2](#) and [Appendix 4](#) for additional details). If a patient discontinues from the study, the patient should be asked if he or she can still be contacted for further information, unless otherwise specified by the local requirements. The outcome of that discussion should be documented in both the medical records and in the eCRF. If lost to follow-up, the investigator should contact the patient or a responsible relative by telephone followed by registered mail or through a personal visit to establish as completely as possible the reason for the withdrawal. A complete final evaluation at the time of the patient's withdrawal should be made with an explanation of why the patient withdrew from the study.

When applicable, patients should be informed of circumstances under which their participation may be terminated at the medical discretion of the investigator without their

consent. Any administrative or other reasons for withdrawal must be documented and explained to the patient.

An excessive rate of withdrawals can render the study non-interpretable; therefore, unnecessary withdrawal of patients should be avoided. Should a patient decide to withdraw, all efforts will be made to complete and report the observations prior to withdrawal as thoroughly as possible.

4.7.3 Study Discontinuation

The Sponsor has the right to terminate this study at any time. Reasons for terminating the study may include, but are not limited to, the following:

- The incidence or severity of adverse events in this or other studies indicates a potential health hazard to patients
- Patient enrollment is unsatisfactory

The Sponsor will notify the investigator if the Sponsor decides to discontinue the study.

4.7.4 Site Discontinuation

The Sponsor has the right to close a site at any time. Reasons for closing a site may include, but are not limited to, the following:

- Excessively slow recruitment
- Poor protocol adherence
- Inaccurate or incomplete data recording
- Non-compliance with the International Council for Harmonisation (ICH) guideline for Good Clinical Practice
- No study activity (i.e., all patients have completed the study and all obligations have been fulfilled)

5. ASSESSMENT OF SAFETY

5.1 SAFETY PLAN

The safety plan for patients in this study is based on clinical experience with ocrelizumab in completed and ongoing studies. The anticipated important safety risks for ocrelizumab are outlined below. Refer to the ocrelizumab local labels and the Ocrelizumab Investigator's Brochure for a complete summary of safety information.

Several measures will be taken to ensure the safety of patients participating in this study. Eligibility criteria have been designed to exclude patients at higher risk for toxicities. Patients will undergo safety monitoring during the study, including assessment of the nature, frequency, and severity of adverse events. In addition, guidelines for managing adverse events, including criteria for dosage modification and treatment interruption or discontinuation, are provided below.

5.1.1 Risks Associated with Ocrelizumab

Important, identified, and potential risks associated with ocrelizumab are described in the approved risk management plan and provided below. Refer to the most recent version of the Ocrelizumab Investigator's Brochure for updates on risks associated with ocrelizumab treatment.

5.1.1.1 Identified Risks and Adverse Drug Reactions Infusion-Related Reactions

All CD20-depleting agents administered via the intravenous route, including ocrelizumab, have been associated with acute IRRs. Following the approved administration regimen (which includes the use of premedication prior to treatment with ocrelizumab to reduce frequency and severity of IRRs), symptoms of IRRs may occur during any ocrelizumab infusion, but have been more frequently reported during the first infusion. Physicians should alert patients that IRRs can occur within 24 hours of the infusion. Across the RMS and PPMS trials, symptoms associated with IRRs included, but are not limited to the following: pruritus, rash, urticaria, erythema, throat irritation, oropharyngeal pain, dyspnea, pharyngeal or laryngeal edema, flushing, hypotension, pyrexia, fatigue, headache, dizziness, nausea, tachycardia and anaphylaxis.

Patients should be observed for at least 1 hour after the completion of the infusion for any symptom of IRR. Patients will be informed about delayed post-infusion symptoms and instructed to contact the study physician if he or she develops such symptoms.

Hypotension, as a symptom of IRR, may occur during ocrelizumab infusions. Therefore, withholding of antihypertensive treatments should be considered for 12 hours prior to and throughout each study drug infusion.

For further guidance on how to manage IRRs refer to the current Ocrelizumab Investigator's Brochure.

Alternative Shorter Infusion of Subsequent Doses

In a study (MA30143, ENSEMBLE Plus) designed to characterize the safety profile of shorter ocrelizumab infusions in patients with RRMS, no differences were found in the frequency and severity of IRRs associated with shorter (2 hour) infusions compared with conventional infusions (3.5 hours). For further details, refer to the current version of the Investigator's Brochure.

Infections

Infection is an identified risk associated with ocrelizumab treatment, predominantly involving mild to moderate respiratory tract infections. Non-disseminated herpes virus-associated infections, mostly mild to moderate, were also reported more frequently with ocrelizumab (approximately 5%–6%, simplex and zoster) than with comparators (approximately 3%).

During the controlled period of the pivotal trials, the proportion of patients with serious infections in RMS was lower in the ocrelizumab group (1.3%) than in the interferon β -1a group (2.9%); in PPMS, the proportion of patients with serious infections was similar in both groups: 6.7% in the placebo group compared with 6.2% in the ocrelizumab group.

Serious, opportunistic and fatal infections have occurred in patients with lupus and rheumatoid arthritis treated with ocrelizumab in Phase III clinical trials. Data from completed studies regarding infection risks with ocrelizumab treatment in these patient populations are provided in the Ocrelizumab Investigator's Brochure.

No opportunistic infections were reported by any patient with MS treated with ocrelizumab during the controlled period of the pivotal trials.

In interventional clinical studies, there were no reports of hepatitis B reactivation in patients with MS treated with ocrelizumab, but it had been reported in 1 patient with rheumatoid arthritis treated with ocrelizumab. HBV screening should be performed in all patients before initiation of treatment with ocrelizumab as per local guidelines. Patients with active HBV should not be treated with ocrelizumab. Patients with positive serology should consult liver disease experts before start of treatment and should be monitored and managed following local medical standards to prevent hepatitis B reactivation.

Delay ocrelizumab administration in patients with an active infection until the infection is resolved.

For PML, see Section [5.1.1.2](#) below.

Impaired Response to Vaccination

After treatment with ocrelizumab for over 2 years in pivotal clinical trials, the proportion of patients with positive antibody titers against *Streptococcus pneumoniae*, mumps, rubella, and varicella were generally similar to the proportions at baseline.

The results of the randomized, open-label Phase IIIb study (BN29739) that assessed if ocrelizumab recipients with RMS raised adequate humoral responses to selected vaccines indicate that patients treated with ocrelizumab were able to mount humoral responses, albeit decreased, to tetanus toxoid; 23-valent pneumococcal polysaccharide; keyhole limpet hemocyanin neoantigen; and seasonal influenza vaccines. The results are summarized in the current version of the Ocrelizumab Investigator's Brochure.

Investigators should review the immunization status of patients being considered for treatment with ocrelizumab. Patients who require vaccination should complete it at least 6 weeks prior to initiation of ocrelizumab. For seasonal influenza vaccines, it is still recommended to vaccinate patients who are on ocrelizumab. Vaccination with live or

live-attenuated vaccines are not recommended during the treatment with ocrelizumab and until B cells have returned to normal levels.

Due to the potential depletion of B cells in neonates and infants of mothers who have been exposed to ocrelizumab during pregnancy, it is recommended that vaccination with live or live-attenuated vaccines should be delayed until B cells have recovered; therefore, measuring CD19-positive B-cell level in neonates and infants prior to vaccination is recommended.

It is recommended that all vaccinations other than live or live-attenuated should follow the local immunization schedule, and measurement of vaccine-induced response titers should be considered to check whether individuals can mount a protective immune response because the efficacy of the vaccination may be decreased.

Decrease in Immunoglobulins

Treatment with ocrelizumab resulted in a decrease in total Ig over the controlled period of the studies, mainly driven by reduction in IgM. The proportion of patients with decrease in Igs below LLN increased over time and with successive dosing. Based on additional patient exposure, in cases of continuous decrease over time, a higher risk of serious infection cannot be ruled out.

Serious Infections Related to Decrease in Immunoglobulins (Patients Previously Exposed to Immunosuppressive/Immunomodulatory Drugs or with Preexisting Hypogammaglobulinemia)

Based on additional patient exposure, an association between decrease in Igs and serious infections with ocrelizumab treatment was observed and was most apparent with IgG. There was no difference in the pattern (e.g., type of infections, latency, duration, outcome) of the serious infections reported in this subset of patients compared to the overall serious infections profile. In addition, risk factors for a subset of patients at higher risk of serious infections could not be identified. Refer to the Ocrelizumab Investigator's Brochure for more details.

Delayed Return of Peripheral B Cells

Treatment with ocrelizumab leads to rapid depletion of CD19+ B cells in blood by 14 days post-treatment (first timepoint of assessment) as an expected pharmacologic effect. This was sustained throughout the treatment period. The longest follow-up duration after the last ocrelizumab infusion from Phase II Study WA21493 in 51 patients indicates that the median time to repletion (returned to baseline/LLN, whichever occurred first) of B cells was 72 weeks (range 27–175 weeks).

5.1.1.2 Potential Risks Malignancies (including Breast Cancer)

An increased risk of malignancy with ocrelizumab may exist. In controlled trials in MS, malignancies, including breast cancer, occurred more frequently in ocrelizumab-treated patients. Breast cancer occurred in 6 of 781 females treated with ocrelizumab and none

of 668 females treated with interferon β -1A or placebo. Patients should follow standard breast cancer screening guidelines.

Refer to the current Ocrelizumab Investigator's Brochure for more details.

If a malignant event is reported, key available information on cancer will be collected for this study and reported as a serious adverse event on the eCRF. Further explorations and detailed cancer information will be solicited via a questionnaire (e.g., further details on tumor diagnostics, grade/staging, and available histopathologic and genetic testing results).

Progressive Multifocal Leukoencephalopathy

John Cunningham (JC) virus infection resulting in PML has been reported very rarely in patients treated with anti-CD20 antibodies, including ocrelizumab, and mostly associated with risk factors such as patient population or polytherapy with immunosuppressants. The reporting rate with ocrelizumab has been approximately 1 case per 100,000 patients. Since the risk of PML cannot be ruled out, physicians should be vigilant for early signs and symptoms of PML, which can include any new onset or worsening of neurological signs or symptoms as these can be similar to an MS relapse. If PML is suspected, dosing with ocrelizumab must be withheld. Evaluation of PML, including MRI scans preferably with contrast (compared with pretreatment MRI scans), confirmatory CSF testing for JC viral DNA, and repeat neurological assessments should be considered. If PML is confirmed, ocrelizumab must be discontinued permanently.

Refer to [Appendix 5](#) for diagnosis guidance of PML. See the Ocrelizumab Investigator's Brochure for more details.

Hypersensitivity Reactions

Hypersensitivity may be difficult to distinguish from IRRs in terms of symptoms. A hypersensitivity reaction may present during any infusion, although typically would not present during the first infusion. For subsequent infusions, more severe symptoms than previously experienced, or new severe symptoms, should prompt consideration of a potential hypersensitivity reaction. If a hypersensitivity reaction is suspected during infusion, the infusion must be stopped immediately and permanently. Patients with known IgE-mediated hypersensitivity to ocrelizumab must not be treated.

Neutropenia

During the controlled treatment period, decreased neutrophils were observed in 12% and 15% of MS patients treated with ocrelizumab in PPMS and RMS, respectively. Most were mild to moderate in severity, approximately 1% of the patients had Grade 3 or 4 neutropenia; and no temporal association with infections was identified. On the basis of additional patient exposure, an association between neutropenia and serious infections with ocrelizumab treatment was not observed. Refer to the Ocrelizumab Investigator's Brochure for more details.

5.1.2 Risks Associated with Corticosteroids

The adverse reactions of corticosteroids may result from unwanted glucocorticoid actions or from inhibition of the hypothalamic-pituitary-adrenal axis. Refer to local prescribing information.

5.1.3 Risks Associated with Antihistamines

The adverse reactions depend on the sedating properties of the antihistamine and include, but are not limited to, nausea, drowsiness, headaches, dry mouth, and allergic reactions such as rash. Refer to local prescribing information.

5.1.4 Management of Patients Who Experience Adverse Events

5.1.4.1 Dose Modifications

Study drug dose modifications are not foreseen.

5.1.4.2 Treatment Interruption

Study drug treatment may be temporarily suspended in patients who experience relevant adverse events considered to be related to study drug and prevent the patient from re-treatment with the study drug (see Section 4.3.2.3 for details on re-treatment criteria).

For female patients who become pregnant during the study, study drug treatment must be withheld for the duration of the pregnancy and breastfeeding. Study drug may be restarted following the delivery/end of breastfeeding, after discussing the risks and benefits of continuing the treatment (see Section 5.4.3).

5.1.4.3 Management Guidelines Infusion-Related Reactions

Slowing of the infusion rate or interruption of the infusion may be necessary in the event of an infusion reaction. In rare cases, ocrelizumab treatment may need to be discontinued. Follow ocrelizumab local label for further guidelines.

Handling of IRRs will depend on the intensity of symptoms (see also Table 6 for grading of intensity of IRRs).

For a **mild to moderate (Grade 1 or 2)** non-allergic, infusion-related event, the infusion rate should be reduced to half the rate being given at the time of onset of the event (e.g., from 50 mL/hr to 25 mL/hr or from 100 mL/hr to 50 mL/hr). Once the event has resolved, the investigator should wait for 30 minutes while delivering the infusion at the reduced rate. If tolerated, the infusion rate may then be increased to the next closest rate on the patient's infusion schedule and the rate increments resumed.

For a **severe infusion-related event (Grade 3)** or a complex of flushing, fever, and throat pain symptoms, the infusion should be interrupted immediately, and the patient should receive aggressive symptomatic treatment. The infusion should be restarted only

after all the symptoms have disappeared. The initial infusion rate at restart should be half of the infusion rate that was in progress at the time of onset of the reaction.

For a **life-threatening infusion-related event (Grade 4)** during an infusion, the infusion should be immediately stopped, and the patient should receive appropriate treatment (including use of resuscitation medications and equipment that must be available and used as clinically indicated). The patient will be withdrawn from treatment and should enter the follow-up phase.

The above examples of dose interruption and slowing (for mild/moderate and severe IRRs) will result in a change in the infusion rate and increase the total duration of the infusion but not the total dose.

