4.3.2.3 Re-Treatment Criteria for Ocrelizumab

Prior to re-treatment, the following conditions must be met:

- Absence of severe allergic or anaphylactic reaction to a previous ocrelizumab infusion

- Absence of any significant or uncontrolled medical condition or treatment-emergent, clinically significant laboratory abnormality
- Absence of active infection
- ANC $\geq 1.5 \times 10^3/\mu\text{L}$
- CD4 cell count $\geq 250/\mu\text{L}$
- IgG ≥ 3.3 g/L
- Negative pregnancy test

In the event of pregnancy, the investigator must counsel the patient as to the risks of continuing with the pregnancy and the possible effects on the fetus. Given there are insufficient, well-controlled data from studies testing the use of ocrelizumab in pregnant or breastfeeding women, all infusions of ocrelizumab must be suspended until the completion of pregnancy and breastfeeding. Pregnant and breastfeeding patients should continue to follow the schedule of activities for the study; however, no infusions will occur. If there is a concern with the ability of a pregnant or breastfeeding patient to perform all scheduled assessments, the investigator must contact the Medical Monitor for further discussion. Restart of ocrelizumab treatment following pregnancy and breastfeeding will be decided as a result of a thorough benefit-risk discussion between the patient and investigator.

If any of these are not met prior to re-dosing, further administration of ocrelizumab must be suspended until resolved or held indefinitely.

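### For a Grade 3 infusion reaction with suspected hypersensitivity, one protocol section provides for a half-rate restart and another requires a permanent stop

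*Protocol*

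**What the plan says.** Protocol section 4.3.2 refers sites to section 5.1.4.3 for modifying, interrupting or discontinuing treatment in patients with adverse events. Section 5.1.4.3 sets its instructions by grade:

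- Grade 1 or 2: the rule is written for a "non-allergic, infusion-related event, the infusion rate should be reduced to half the rate being given at the time of onset of the event".
- Grade 3: for a severe event "or a complex of flushing, fever, and throat pain symptoms, the infusion should be interrupted immediately, and the patient should receive aggressive symptomatic treatment". Restart is allowed only when every symptom has gone, and "The initial infusion rate at restart should be half of the infusion rate that was in progress at the time of onset".
- Grade 4: the infusion is stopped and the patient is withdrawn from treatment.

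Section 5.1.1.2, under Hypersensitivity Reactions, begins "Hypersensitivity may be difficult to distinguish from IRRs in terms of symptoms". It adds that at later infusions, severe symptoms that are new or worse than before should make the site consider hypersensitivity. It then says: "If a hypersensitivity reaction is suspected during infusion, the infusion must be stopped immediately and permanently". Patients with known IgE-mediated hypersensitivity to ocrelizumab are barred from treatment.

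Two other sections bear on later dosing. Section 4.3.2.3 makes the absence of a severe allergic or anaphylactic reaction to an earlier infusion a condition of re-dosing. If a condition is not met, "further administration of ocrelizumab must be suspended until resolved or held indefinitely". Section 4.7.1 lists specific circumstances for withdrawal, and the only infusion-related one is the life-threatening category, "Grade 4) infusion-related event that occurred during a previous ocrelizumab infusion".

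**The concern.** Both rules apply while the drug is running, on a potential risk that the protocol itself names. A site that follows 5.1.4.3 as written could restart an infusion that 5.1.1.2 says must not be resumed. The section that sites are sent to is the one without the stop rule.

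The later path may also differ by site. Withdrawal from treatment leads to a discontinuation visit, the FU1 phase and no open-label extension (protocol 3.1.1.4, 3.1.1.5 and 4.7.1). Suspension leaves the patient in the double-blind phase with a missed dose.

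**Working it through.** There is no figure to reproduce; the check is a comparison of texts. The two in-infusion rules side by side:

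| | 5.1.4.3, Grade 3 | 5.1.1.2, hypersensitivity |
|---|---|---|
| Trigger | severity of an infusion-related event, or a named symptom complex | suspicion of hypersensitivity |
| Severity limit | Grade 3 or the symptom complex | none stated |
| Allergic events excluded? | no | not applicable |
| First action | interrupt and treat | stop |
| After symptoms clear | restart at half rate | no resumption |
| Refers to the other section? | no | no |

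1. **Can one event meet both triggers?** Yes. One trigger is a grade and the other is a suspected cause, so they do not exclude each other. Section 5.1.1.2 says the presentations are hard to separate. Section 5.1.1.1 reports throat irritation, laryngeal edema and, at the end of its list of infusion-reaction symptoms, "flushing, hypotension, pyrexia, fatigue, headache, dizziness, nausea, tachycardia and anaphylaxis". An example is a new severe reaction with throat symptoms at a later infusion. It is Grade 3 under 5.1.4.3. It also meets the prompt in 5.1.1.2 to consider hypersensitivity, and if the site then suspects hypersensitivity, the stop rule applies as well.

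2. **Does 5.1.4.3 keep the two apart?** Only for Grade 1 or 2, where the rule is limited to events that are not allergic. The Grade 3 rule has no such limit. The section closes by saying that interruption and slowing change the rate and duration but not the total dose, so it expects the infusion to be completed.

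3. **Are the outcomes compatible?** The first step is, since both sections halt the infusion. The second is not: one provides for restart and the other rules it out.

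4. **Do the later-dosing sections settle it?** No. Section 4.3.2.3 offers two consequences, and a past reaction, as a fact of history, cannot resolve. An indefinite hold would fit a permanent stop, but the text does not say that this branch applies. Section 5.1.4.2 cites the same criteria when describing temporary suspension. Section 4.7.1 has no hypersensitivity item, although its investigator-judgement criteria can cover one. Section 5.1.1.2 itself stops the infusion without saying whether study treatment also ends, apart from the IgE-mediated case.

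5. **How often can it arise?** The double-blind phase has 6 doses, the first split in two, so 2 + 5 = 7 infusions per patient, plus every post-double-progression and open-label infusion. About 1000 patients are randomized 1:1, so about 1000 / 2 = 500 receive ocrelizumab in the double-blind phase. These are occasions on which an event could occur. The documents give no rate of Grade 3 infusion reactions or of suspected hypersensitivity, so no count follows.

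6. **Does it reach the analysis?** Hardly, for the primary endpoint. Under SAP 4.2.2, withdrawal without another MS therapy or commercial ocrelizumab follows a treatment-policy strategy, and FU1 keeps EDSS and 9-HPT every 12 weeks. For the two MRI secondary endpoints (SAP 4.3.2 and 4.3.3), data after treatment discontinuation are set to missing, with discontinuation dated 24 weeks after the last dose (SAP 4.1). A patient recorded as withdrawn therefore loses later scans that a suspended patient keeps. The size of this effect is unknown.

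**The case against.** The strongest reply is that the rules answer different questions. Section 5.1.4.3 manages infusion reactions by grade, and 5.1.1.2 takes over once hypersensitivity is suspected. The second is more specific and is worded as mandatory, while the first is a guideline. New or worse symptoms call only for consideration of hypersensitivity; the stop needs suspicion. The restart sentence can be read as a precondition more than an order. Section 5.1.4.3 also defers to the local label, and 5.1.1.1 to the Investigator's Brochure, neither of which is available here.

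Much of this is fair, and it narrows the point to events where hypersensitivity is actually suspected. It does not remove the conflict. The protocol nowhere says that 5.1.1.2 prevails, and a reader of 5.1.4.3 is not told that the other rule exists. The label is cited for further guidance, not to rank the protocol's own sections.

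A reader might go further and see three incompatible rules, counting 4.3.2.3 as the third. The text does not support that. Section 4.3.2.3 applies before the next dose and not during an infusion, and its full wording includes an indefinite hold, which is compatible with a permanent stop. A reader might also infer that 4.7.1 blocks withdrawal below Grade 4. It does not: it requires discontinuation for any condition that the investigator judges may endanger the patient.

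**Conclusion.** Two stated rules conflict for one class of event: a Grade 3 infusion reaction in which hypersensitivity is also suspected. This is a patient-safety inconsistency in the protocol's instructions and more than a missing detail. The unclear branch in 4.3.2.3 and the absent item in 4.7.1 are secondary ambiguities.

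It would be wrong to infer that every Grade 3 event is affected. Section 5.1.1.2 says hypersensitivity typically does not present at the first infusion, whereas 5.1.1.1 says infusion reactions are reported more often there. The number of affected patients cannot be derived. It would also be wrong to infer a material threat to the primary result. The conclusion that the effect there is small assumes that withdrawn patients stay in FU1 and do not start another MS therapy.

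The symptom list in 5.1.1.1 reports what was seen across earlier trials. It is not a classification rule and needs no change for this purpose.

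**What to change.** The sponsor should reconcile the sections in this order:

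1. In 5.1.4.3, state whether the Grade 3 restart rule applies when an allergic or hypersensitivity reaction is suspected, and which section governs when both triggers are met. Add cross-references between 5.1.4.3 and 5.1.1.2.
2. In 4.3.2.3, state which of the two consequences applies after a severe allergic or anaphylactic reaction to an earlier infusion.
3. Make the withdrawal list in 4.7.1 agree with that decision, including whether a permanent stop of the infusion also ends study treatment.

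The choice of clinical rule belongs to the sponsor's safety physicians, and this review takes no position on it. The cost is protocol wording and a memo to sites. No new procedure, data item or staff is needed.
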